9.2.3. Assessment of Severity

The PI, or delegated clinician, should make an assessment of severity for each AE according to the following Clavien Dindo [56] criteria as shown in the table below:

Grade	Definition
I	Any deviation from the normal postoperative course without the need for pharmacological treatment or surgical, endoscopic, and radiological interventions Allowed therapeutic regimens are: drugs as antiemetics, antipyretics, analgesics, diuretics, electrolytes, and physiotherapy. This grade also includes wound infections opened at bedside.
II	Requiring pharmacological treatment with drugs other than such allowed for grade I complications Blood transfusions and total parenteral nutrition are also included
III Requi	ring surgical, endoscopic or radiological intervention:
Illa	Intervention not under general anaesthesia
IIIb	Intervention under general anaesthesia
IV Life t	hreatening complication (including CNS complications)* requiring IC/ICU management:

Grade	Definition
IVa	Single organ dysfunction (including dialysis)
IVb	Multiorgan dysfunction
V	Death of a patient

^{*}Brain hemorrhage, ischemic stroke, subarrachnoidal bleeding, but excluding transient ischemic attacks.

9.2.4. Assessment of Seriousness

The PI, or delegated clinician, should make an assessment of seriousness against the standard definition in the Safety Reporting Definitions section 9.1.

9.2.5. Assessment of Causality

The relationship between the intervention and the occurrence of each AE must be assessed and categorised by the PI or delegated clinician using clinical judgement to determine the causal relationship. Other factors such as medical history of underlying diseases, concomitant therapy and any other relevant risk factors should be considered. The assessor should also consult the expected events in section 9.3.1. If there is any doubt, the CI may be consulted. The following definitions should be used:

Yes (related) The event is considered related or possibly related to the

intervention

No The event is not considered related to the intervention

9.3. Expedited Safety Reporting

The safety profile of the four interventions is well-established within this patient population and a list of expected events can be found in section 9.3.3. Immediate reporting of expected SAEs to the Sponsor is not required, only unexpected SAEs related to the intervention require expedited safety reporting. All adverse events (including expected and unexpected SAEs) should be recorded in the eCRF (Sealed Envelope) and will be reviewed by the Data Monitoring Committee on a regular basis (see section 13.1).

9.3.1. Reporting SAEs

Where an AE is assessed as serious, related to the intervention and unnexpected according to the protocol section 9.3.3, it must be reported immediately. Unexpected, related serious adverse

events, URSEs should be reported from the point of surgical intervention until six months postsurgery.

Please send completed SAE report forms via secure email to:

[contact]

This is a distribution list to ensure that all relevant individuals (CI, NCTU trial management and QA management personnel and Sponsor) are informed of the event in a timely manner. All confirmed URSEs will be allocated a unique code number and a confirmation of receipt returned to the sender. URSEs will be recorded by trial management personnel on the trial's safety database.

To ensure adherence with the required reporting timeframes, sites must notify NCTU of URSEs immediately but no later than 24 hours after becoming aware. Information should be submitted on an SAE report form via secure e-mail. Examples of secure email include nhs.net and nhs.uk where listed as accredited to the DCB1596 secure email standard, (https://digital.nhs.uk/services/nhsmail/the-secure-email-standard). Where it is not possible to send a report via a secure e-mail, the report should be sent encrypted.

Preliminary reporting to NCTU via email or telephone is acceptable in order to meet the 24 hour reporting timeline, where circumstances do not allow for immediate completion of the SAE form. However the SAE form should be completed and submitted as soon as possible after the initial notification in order to comply with reporting timelines.

For each URSE the following information will be collected:

- Event term
- Full details in medical terms and case description
- Event duration (start and end dates, if applicable)
- Severity
- Action taken
- Outcome
- Seriousness criteria
- Causality & Expectedness in the opinion of the investigator

In the case of incomplete information at the time of initial reporting, or change of condition or follow up information, a follow up report form must be completed and sent via secure email as soon as possible. All URSEs will be followed up until resolution, or until the participant reaches the end of the study. An URSE is considered to have resolved if the outcome has been classed as:

- Completely Recovered
- Recovered with Sequelae
- Condition stable and no change anticipated
- Participant Died

The assessment of causality and expectedness will undergo documented review by the PI and CI for each URSE.

If a participant withdraws from the study due to an URSE, the trial team should continue to follow up the event until the URSE has resolved or stabilised.

9.3.2. Exclusions to SAE reporting

Any AEs that are serious and not-related to the intervention, or that are serious, related to the intervention and expected (as per protocol section 9.3.3.) do not require immediate (24-hour) reporting. Events that are excluded from recording as an AE for the study should not be reported as SAEs i.e. SAEs not related to the condition or the intervention, including death (see section 9.5). Planned hospital admissions for the study intervention are also excluded from safety reporting.

9.3.3. Assessment of Expectedness

All related serious events (SAEs determined as having reasonable suspected causal relationship between the event and the study intervention) will be assessed for expectedness by both the PI and the CI using the list of expected events below:

TURP		
Bladder/ abdominal pain	Retained fragments	
Bladder neck stenosis	Retrograde ejaculation	
Bladder perforation	Return to theatre for bladder wash out for	
Capsular perforation	bleeding	
Clot retention	Stress incontinence	
Dysuria	TUR-syndrome	
Erectile dysfunction	Urethral stricture	
Haematuria	Urinary frequency	
Hemorrhage	Urinary incontinence	
Injury to the urethra	Urinary retention	
Passage of debris in urine	Urinary tract infection	
Passing of clots in urine	Urosepsis	
Penile pain		

Rezum

Dysuria Return to theatre for resection of prostate

Erectile dysfunction Sediment / debris in urine

Haematuria Urethral stricture

Hematospermia Urinary frequency
Pain or discomfort in the pelvic area Urinary incontinence

Passing of clots

Penile pain

Prostate abscess

Urinary leakage

Urinary retention

Urinary tract infection

Retrograde ejaculation Urinary urgency

iTIND

Bladder neck stricture Penile pain
Bladder perforation Pyrexia

Changes to erectile function Retrograde ejaculation

Dysuria Return to theatre for wash out / bleeding
Haematuria Removal required under general anesthetic

Haematuria Removal required under general a
Hematospermia Urethral stricture
Hemorrhage Urinary frequency

Inflammation to the bladder neck
Urinary hesitancy
Urinary incontinence

Irritation to the meatus Urinary leakage / incontinence

Local irritation

Pain or pressure in the perineal area

Urinary retention

Urinary tract infection

Pelvic discomfort Urinary urgency

PUL

Retrograde ejaculation

Dysuria Return to theatre for wash out / bleeding

Erectile dysfunction

Temporary urinary urge incontinence

Haematuria

Urethral stricture

Implant encrustation

Misfire of implant / Bone strike

Urinary incontinence
Urinary leakage

Pain or discomfort in the pelvic area

Urinary retention

Passage of clots/ debris

Urinary tract infection

Passage of clots/ debris Urinary tract infection

Pelvic haematoma Urinary urgency

[figure not shown]
Penile pain

Anesthesia associated events				
Allergic reaction	Nausea & Vomiting			
Aspiration	Nerve injury			
Chest infection	Pain and conscious awareness			
Death	Paralysis			
Deep Vein Thrombosis	Pulmonary embolus			
Drug reaction	Sore throat and hoarse voice			
Heart Attack	Spinal haematoma			
Local inflammation / skin reactions / cellulitis	Stroke			

9.3.4. Safety Reporting Summary Table

Event	Required actions	
Adverse Event	Record in eCRF	
SAE that is related to BPE, condition progression or treatment failure	Record in eCRF and mark as serious	
SAE that is related to the intervention and is expected (as per protocol section 9.3.1)	Record in eCRF and mark as serious	
SAE that is related to the intervention and is unexpected (as per protocol section 9.3.1)	Record in eCRF and mark as serious Report immediately to NCTU as a suspected URSE on an SAE Report Form via secure email	
(Serious) Adverse Event not related to intervention, BPE, condition progression or treatment failure	None (will not be collected for this study)	

9.3.1. Safety Reporting Diagram

Contact details for reporting SAEs

Please send SAE form(s) via secure email to [contact]

9.4. Reporting URSEs to the REC

All URSEs occurring from the intervention until six months post-trial intervention must be reported to the NHS Research Ethics Committee (REC). The NCTU will perform this reporting and notify the Sponsor.

URSEs must be reported no later than 15 calendar days after the NCTU has first knowledge of the event. Any relevant follow-up information should be sought and reported as soon as possible after the initial report.

The reporting timeframe starts at day 0 when the NCTU is in receipt of a minimum set of information:

- Sponsor trial reference and trial name (sponsor reference)
- Patient trial number
- Name of intervention
- Date of notification of the event
- Medical description of the event
- Causality assessment
- Seriousness of the event, particularly if life threatening or fatal
- An identifiable reporter (e.g., Principal Investigator)

The site is expected to co-operate fully with NCTU and Sponsor staff, to ensure that a full and detailed report is submitted to the REC within the required timelines. PIs will be informed of all URSEs by NCTU.

9.5. Notification of Deaths

AEs with an outcome of death, that are related to the study intervention and unexpected will be reported as an URSE to NCTU on an SAE form. Other deaths resulting from AEs that are either related to the intervention and expected, or are related to BPE, condition progression, or treatment failure will be recorded in the eCRF and marked as 'serious'. Deaths for reasons that do not meet the criteria to be recorded as an AE (as described in 9.2.2.) will not be recorded in the eCRF

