7.5.5.5. EQ-5D-5L

EQ-5D-5L [52] is a patient completed five item, validated general quality of life measure from which health utility can be calculated. This is a score within the range 0 to 1 for quality of life, where (0) is equivalent to death and (1) represents perfect health.

The EQ-5D-5L consists of two pages: the EQ-5D descriptive system and the EQ visual analogue scale (EQ VAS):

The EQ VAS records the patient's self-rated health on a vertical visual analogue scale, where the endpoints are labelled 'The best health you can imagine' and 'The worst health you can imagine'. The VAS can be used as a quantitative measure of health outcome that reflect the patient's own judgement.

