9.2. Adverse Events

9.2.1. Recording Adverse Events

It is intended that all AEs occurring from the point of surgical intervention until six months postsurgery possibly associated with BPE, condition progression, intervention or treatment failure are collected as adverse events. These events must be recorded in the trial database eCRF and recorded in the participant's medical notes as part of their ongoing care. The Clavien Dindo criteria in section 9.2.3. should be used for Assessment of Severity.

All intraoperative AEs will be recorded and identified via a question in the Operative Parameters form and post-operative AEs will be patient reported by an adverse events questionnaire administered at the telephone call at six weeks and six months post-surgery or identified through medical records.

The documentation of each AE should include an event term, event duration (start and stop dates) and details of any action taken or treatment in response to the event. Each AE must be assessed by the site PI or delegated investigator for severity (section 9.2.3.), seriousness (section 9.2.4.) and causality (section 9.2.5.).

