9.2.2. Exclusions to Adverse Events reporting

For the purposes of this trial, AEs not related to the condition or the intervention will not be collected, including but not limited to hospitalization for the non-related conditions.

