10.3.6. The Within Trial Analysis (WTA)

The base case within trial analysis will compare changes in health-related QoL, based on responses to the EQ-5D-5L at baseline, six weeks, six and 12 months. Responses to the EQ-5D-5L will be combined with a UK tariff that is relevant at the time the study reports and used to estimate QALYs. The results of the analyses will be presented as point estimates of mean incremental costs and QALYs. An adjusted analysis will be used to estimate the point estimates of the mean incremental costs, effects and cost-effectiveness using seemingly unrelated regression (SUR). We will explore the uncertainty in estimates of cost-effectiveness through a stochastic sensitivity analysis drawing bootstrapped samples of mean costs and mean QALYs. Results from this analysis will be combined willingness-to-pay (WTP) threshold values generating cost effectiveness acceptability curves (CEACs) that represent the probability of the interventions being cost-effective at each WTP value. As part of the CEA we will also estimate the distribution of costs and health benefits (QALY gains) by socio-economic status using IMD data.

Secondary analysis will be conducted and the cost-effectiveness analysis will be replicated at two and three years post-intervention.

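### Deaths judged unrelated are kept out of the eCRF and no vital-status item exists, so complete all-cause mortality by arm is not available as planned and QALYs may treat deaths as missing

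*Protocol*

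**What the plan says.** Four places in section 9 of the protocol state the same rule.

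- 9.2.2 limits collection: "AEs not related to the condition or the intervention will not be collected".
- 9.3.2 carries the exclusion over to serious events and names death: "SAEs not related to the condition or the intervention, including death (see section 9.5".
- The summary table in 9.3.4 gives the action for an unrelated (serious) adverse event as "None (will not be collected for this study".
- 9.5 closes the matter as far as the eCRF is concerned: "Deaths for reasons that do not meet the criteria to be recorded as an AE (as described in 9.2.2.) will not be recorded".

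Some deaths are recorded. Under 9.5, a related and unexpected death is reported as a URSE. Deaths that are related and expected, or due to BPE, progression or treatment failure, go into the eCRF marked as serious. The AE window in 9.2.1 is limited, however: "It is intended that all AEs occurring from the point of surgical intervention until six months postsurgery possibly associated with BPE". Follow-up runs to three years (section 4). The schedule of events (7.12) has no row for vital status or date of death.

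On the economic side, 7.5.5.5 sets the utility scale, "where (0) is equivalent to death and (1) represents perfect health", and 10.3.6 builds QALYs from it: "Responses to the EQ-5D-5L will be combined with a UK tariff". The base case is at 12 months and the analysis is repeated at two and three years. Section 10.3.8 leaves imputation of missing economic data open until the full dataset is available.

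**The concern.** All-cause mortality by arm is the one safety measure that needs no attribution. Here, whether a death is recorded depends on attribution. The trial is open-label (section 4) and causality is assessed locally (9.2.5). The Chief Investigator's causality review in 9.8 covers related SAEs, so a death that the site calls unrelated has no required second look. It is also absent from the eCRF events that 9.3 sends to the DMC. If the threshold for calling a death unrelated differs between TURP and the minimally invasive arms, recorded mortality will differ for that reason alone.

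Deaths outside the window have no AE route at all. That covers deaths after six months, even related ones, and deaths while waiting for surgery. Section 7.4 says the wait may be up to a year for TURP.

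Three uses of the data are affected: safety oversight, the split of attrition into death and dropout when the missing-data assumption in 10.3.3 is judged, and the QALYs. An analysis plan can decide how to handle deaths, but it cannot supply deaths and dates that the protocol says not to record.

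**Working it through.** **The trial's own figures, used for scale.** Inputs from 10.2: SD 6.3, margin 3, one-sided alpha 0.0195, power 90%, attrition 25%.

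- Normal approximation: n = 2 × 6.3² × (2.064 + 1.282)² / 3² = 98.7, so 99 per intervention. The noncentral t calculation gives 100 (power 0.9006; 99 gives 0.8976). This matches the stated 100.
- 100 / 0.75 = 133.3, so 134. Then 4 × 134 = 536. Both match. The sample size is not in dispute.

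**Is there another route to the deaths?**

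| Route | What it offers | Gap |
|---|---|---|
| Withdrawal or discontinuation reason in the eCRF (7.13) | A reason field | Death is not named as a reason |
| Routine NHS data (7.13.1) | Data to three years | Described for men who withdraw, with consent sought on the withdrawal form; the list it points to has no vital status |
| Consent to long-term notes review (7.1.2) | Access to notes | No vital-status check is planned |

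Some deaths could be found by these routes. None is planned to find all of them.

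**Size.** The only mortality figure in the protocol is peri-operative, up to 0.25% for resection-type surgery (section 1). All-cause mortality is therefore assumed: m = 0.5% to 3% a year, constant hazard λ = -ln(1 - m), with utility while alive u = 0.7 to 0.9.

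- Expected deaths by year T among N men: N × [1 - (1 - m)^T].
- Overstatement of mean QALYs if every death is treated as alive rather than utility 0: u × [T - (1 - e^(-λT)) / λ].
- Example with m = 1%, u = 0.8, T = 3: λ = 0.01005, (1 - 0.9703) / 0.01005 = 2.955, and 0.8 × (3 - 2.955) = 0.036.

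| m per year | Deaths per 134, 1 y / 3 y | Deaths per 536, 1 y / 3 y | QALY overstatement, 1 y | QALY overstatement, 3 y |
|---|---|---|---|---|
| 0.5% | 0.7 / 2.0 | 2.7 / 8.0 | 0.0018-0.0023 | 0.0157-0.0202 |
| 1% | 1.3 / 4.0 | 5.4 / 15.9 | 0.0035-0.0045 | 0.0313-0.0403 |
| 2% | 2.7 / 7.9 | 10.7 / 31.5 | 0.0070-0.0090 | 0.0624-0.0802 |
| 3% | 4.0 / 11.7 | 16.1 / 46.8 | 0.0106-0.0136 | 0.0931-0.1197 |

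**Effect on the comparison.** With equal mortality and equal recording, the overstatement cancels between arms. For a difference d in 12-month mortality, with death at mid-year and u = 0.8, the incremental QALY shifts by d × 0.5 × 0.8. That is 0.004, 0.008 and 0.012 for d = 1, 2 and 3 percentage points. At three years, a 2-point difference with 1.5 years lost per death gives 0.02 × 1.5 × 0.8 = 0.024.

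**Share of attrition.** The plan allows 134 - 100 = 34 losses per arm. The 0.7 to 4.0 expected deaths by 12 months would be about 2% to 12% of these.

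**The case against.** The best defence is that the QALY damage is limited. Within each randomisation scheme, truly unrelated deaths should be balanced, so their effect largely cancels. Deaths caused by treatment should mostly be recorded, because the threshold is low: 9.2.1 takes events possibly associated with the condition or intervention, 9.2.5 counts possibly related as related, and 9.3.3 lists death as an expected anaesthesia event. The primary economic outcome is at 12 months, where the error is small, and men with a predicted life expectancy under three years are excluded (6.2). All of this stands. It leaves misjudged relatedness and deaths outside the six-month window.

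A reader might infer more than the protocol supports:

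- *That the QALY analysis is wrong.* Section 10.3.8 leaves imputation open, and nothing says a dead man will be imputed as alive. How deaths enter the QALYs is commonly left to an analysis plan, so silence on that is no fault. The supportable point is that the dates may not be there to use.
- *That mortality cannot be reported, or that every dead man will look like a dropout.* Withdrawal reasons and consented notes review could reveal some deaths. Complete ascertainment is unplanned, not impossible.
- *That the time-to-event analyses have no censoring date.* Those models are optional in 10.3.2, and the last completed contact remains usable. Only the date of death is lost.
- *That routine NHS data already cover this.* Section 7.13.1 provides for such data only for men who withdraw.

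**Conclusion.** The point holds as a should-fix. Four consistent passages keep deaths judged unrelated out of the eCRF, the AE window closes at six months, and no vital-status item exists. As planned, complete all-cause mortality by arm is not available, and deaths cannot be reliably separated from loss to follow-up.

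The QALY consequence is a risk of bias. Under the assumed mortality and utility it is small at 12 months and larger at two and three years. It reaches the between-arm comparison only if mortality, or the recording of it, differs by arm. These sizes rest on assumptions, since the protocol gives no all-cause mortality, and they are an upper bound in that every death is taken to be unrecorded and treated as alive. Nothing here shows that the I-PSS conclusion or the 12-month economic result would change, so a higher grade is not earned. The safety-oversight argument does not depend on these assumptions.

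**What to change.** Replace the last sentence of 9.5 with: *All deaths from randomisation to three years, whatever the cause, will be recorded in the eCRF with date and cause.* Align 9.3.2 and 9.3.4 with it, and add a vital-status row to the schedule in 7.12.

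Ascertain deaths at each follow-up contact and by the notes review already consented to (7.1.2). Report all-cause mortality by arm to the DMC and in the final report. In the QALY calculation, set utility to 0 from the date of death. The expedited reporting rules and the exclusion of other unrelated AEs can stay as they are.

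Cost: a wording amendment, one extra eCRF form, and a brief vital-status check at the two- and three-year contacts. Those contacts are remote questionnaires only, so non-response there should prompt the notes review.

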9.6. Pregnancy Reporting

Reporting of pregnancy of partners of participants is not required for this trial.

9.7. Reporting Urgent Safety Measures

An Urgent Safety Measure (USM) is an action that the Sponsor or an Investigator may take in order to protect the subjects of a trial against any immediate hazard to their health or safety. Upon implementation of an USM by an Investigator, NCTU must be notified immediately and details of the USM given. The NCTU must inform the NHS REC within three days of the USM taking place in accordance with the Sponsor's standard operating procedures.

9.8. Responsibilities

Principal Investigator

- Ensuring that AEs are recorded in line with the requirements of the protocol.
- Using medical judgement in assessment of severity, seriousness and causality of AEs.
- Perform assessment of expectedness of all intervention-related SAEs
- Ensuring that all URSEs, are recorded and reported to the Sponsor within 24 hours of becoming aware of the event and provide further follow-up information as soon as available.
- These tasks may be delegated to a member of the research team, but the PI retains overall responsibility.

Chief Investigator

- Clinical oversight of the safety of trial participants, including an ongoing review of the risk/benefit
- Using medical judgement in assessment of severity, seriousness and causality of SAEs where it has not been possible to obtain local medical assessment.
- Perform assessment of causality and expectedness of all related SAEs on behalf of Sponsor.
- Immediate review of all URSEs.
- Review of specific SAEs and URSEs in accordance with the trial risk assessment and protocol.
- Review/assignment of Medical Dictionary for Regulatory Activities (MedDRA) or body system coding for all AEs and SAEs.
- Reviewing expected events at least annually

Sponsor

- Data collection and verification of all AEs onto a database (may be delegated to NCTU).
- Assessment of expectedness of any related serious events (may be delegated to CI).
- Expedited reporting of URSEs to the REC within required timelines (may be delegated to NCTU).
- Reporting of USMs to REC within required timeline (may be delegated to NCTU).
- Notification of all investigator sites of any URSE that occurs (may be delegated to NCTU).
- Reporting safety information to the independent oversight committees for the ongoing assessment of the risk/benefit ration throughout the life of the trial (may be delegated to NCTU).

TSC/DMC

Review of safety data collected to date to identify any trends

